#### Phase II:

The efficacy endpoint will be pathologic complete response rate (pCR) as determined at the time of surgery assuming that the trial continues through both stages. For this cohort, the pCR rate at the time of surgery which is after RT, pembrolizumab and, in most cases, chemotherapy will be determined. A significance of 0.05 will be used to declare statistical significance. Data from 50 evaluable patients achieve 80% power to detect an effect size

of 1.20 using a two-sided paired t-test at the 0.05 level of significance compared to the historical pCR rate for triple negative breast cancer. The effect size is defined as the difference between the mean pCR rate for this trial compared to historical data for triple-negative breast cancer. This is equivalent to an absolute difference of 20% between the mean pCR rate between the two groups assuming a standard deviation (SD) of 15%.

Comparisons of clinical characteristics for this cohort will be conducted using descriptive summary statistics using median and range. Changes in TIL score, immune populations, gene expression, microbiome populations and cytokine expression will be compared between different time points and responder/non-responder groups if sufficient numbers for analysis are available using the paired t-test or Wilcoxon sign test depending on the distribution of the data.

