**Table 9.2.3 Stopping rules based on seven interim looks**

Number of Patients	Number to Continue	Probability to Stop	Cumulative Probability to Stop
3	2	0.008	0.008
6	3	0.013	0.021
9	4	0.010	0.031
12	5	0.007	0.038
15	6	0.005	0.044
18	7	0.004	0.047
20	8	0.009	0.048

**Table 9.2.4 Design operating characteristics under different scenarios for the true probability of  $P_d$  for TNBC cohort**

True Value of $P_d$	Probability to Stop	Expected N	Expected N given that we Stopped
0.10	0.003	19.96	6.48
0.30	0.233	17.76	10.38
0.50	0.834	11.01	9.28
0.60	0.967	8.11	7.70

The co-primary efficacy endpoint will be change in TILs. TILs will be assessed in paraffin embedded samples after the study is completed and will have no bearing on impact on continued enrollment for the trial. For each cohort, the mean percent change in TIL score before treatment and after pembrolizumab alone  $\mu_1$  will be compared to the mean change in TIL score before treatment and after pembrolizumab plus radiation  $\mu_2$  using the paired t-test or Wilcoxon sign test depending on the distribution of the data. A significance of 0.05 will be used to declare statistical significance. Let  $SD(\text{diff})$  be the standard deviation of the difference in percent change in TIL score before treatment and after pembrolizumab and before and after treatment with pembrolizumab and radiation. Data from 8 evaluable patients in the HR+ cohort achieve 80% power to detect an effect size of 1.16 using a two-sided paired t-test at the 0.05 level of significance. The effect size is defined as the difference between the two means divided by  $SD(\text{diff})$ ,  $(\mu_1 - \mu_2) / SD(\text{diff})$ . This is equivalent to an absolute difference of 20% between the mean change in TIL scores assuming an  $SD(\text{diff})$  of 17%. For the TNBC cohort, assuming 16 patients are evaluable, the effect size that is detectable with the same power and type I error is 0.75.

Comparisons of clinical characteristics among cohorts will be conducted using descriptive summary statistics using median and range. Changes in TIL score will be compared between cohorts using Fishers exact test.

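### The Phase II pCR power statement in section 9.2.1 does not follow from its own inputs, names a paired test where there are no pairs, and cannot be reconciled with the 40-patient rule in section 9.1

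*Combined protocol and SAP*

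**What the plan says.** Section 9.2.1, Phase II, makes pCR at surgery the efficacy endpoint, "assuming that the trial continues through both stages", and sets significance at 0.05. Its power statement opens: "Data from 50 evaluable patients achieve 80% power to detect an effect size". The effect size is then put at 1.20, the test is a two-sided paired t-test at 0.05, and the comparator is a historical TNBC pCR rate. It adds: "This is equivalent to an absolute difference of 20% between the mean pCR rate between the two groups". The SD behind that equivalence is taken to be 15%. The historical rate is not given there; a reference is cited instead.

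Section 9.1, Phase II, describes a Simon two-stage design. The null is a 10% response rate with a one-sided alternative. Accrual stops if 2 or fewer of the first 22 patients respond; otherwise it continues to 40, and the null is rejected at 8 or more responses. The stated type I error is 0.04, and the stated power is 0.80 at a true rate of 25%.

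Other relevant places:
- The Study Schema allots 10 TNBC patients to Phase Ib and 40 to Phase II.
- Section 1.3.2 puts pCR with current chemotherapy at about 50% and says Phase II will compare pCR with the best available chemotherapy.
- pCR is listed as a secondary objective in section 2.2 and again as exploratory in section 2.3.

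**The concern.** An effect size of 1.20 is very large, and a paired t-test in 50 patients would have far more than 80% power to detect it. The power statement therefore cannot be right on its face. The named test also does not suit the data: Phase II is a single arm, and each patient contributes one binary pCR result.

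The reader is left with two tests for the same endpoint. One is two-sided, against an unstated historical rate, in 50 patients. The other is one-sided, against 10%, in 40 patients. They answer different questions and could lead to opposite conclusions. Success under 9.1 needs 8/40 = 20%, which is 30 points below the roughly 50% reported for chemotherapy, although pCR is measured after RT, pembrolizumab and, "in most cases, chemotherapy will be determined". If the choice is left open, the test and the null could be picked once the results are known.

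**Working it through.** **Inputs.** From 9.2.1 Phase II: n = 50, effect size 1.20, difference 20 points, SD 15 points, two-sided 0.05, paired t-test. From 9.1: 22 + 18 = 40 patients, stop at 2 or fewer of 22, reject at 8 or more of 40. From 1.3.2: about 50% pCR with chemotherapy.

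**1. The formula reproduces the plan's other power statements.** Paired-t power uses the noncentral t distribution with n − 1 degrees of freedom and noncentrality d√n. For the TIL endpoint the plan says "Data from 8 evaluable patients in the HR+ cohort achieve 80% power to detect an effect size of 1.16 using a two-sided paired t-test", and for TNBC "assuming 16 patients are evaluable, the effect size that is detectable with the same power and type I error is 0.75". The formula gives power 0.803 at n = 8, d = 1.16 and 0.801 at n = 16, d = 0.75. Both statements are correct.

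**2. The same formula applied to the pCR statement.**

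| n | d | Power, two-sided 0.05 |
|---|---|---|
| 7 | 1.20 | 0.754 |
| 8 | 1.20 | 0.828 |
| 50 | 1.20 | > 0.999999 |
| 50 | 0.404 | 0.80 |

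At n = 50, 80% power corresponds to d = 0.404, and 0.404 × 15 = 6.1 points, not 20. Other readings do not rescue the figure. One-sided paired tests, 40 in place of 50, and two-sample tests were tried. The lowest power found was 0.959 (20 against 20, two-sided, d = 1.20).

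**3. The ratio.** 20/15 = 1.33. An effect size of 1.20 would need an SD of 20/1.20 = 16.7 points or a difference of 1.20 × 15 = 18 points.

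**4. The SD.** A yes/no outcome has SD √(p(1 − p)): 0.30 at 10%, 0.433 at 25%, 0.50 at 50%. An SD of 0.15 occurs only at p = 0.023 or 0.977.

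**5. The 9.1 rule, exact two-stage binomial.**

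| True rate | P(reject) | P(stop at stage 1) |
|---|---|---|
| 10% | 0.0398 | 0.620 |
| 25% | 0.803 | 0.061 |
| 30% | 0.936 | 0.021 |
| 40% | 0.997 | 0.0016 |
| 50% | 0.9999 | 0.00006 |

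The first two rows confirm the type I error and power stated in 9.1.

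**6. What a 20-point gain would need.** The historical rate is not printed in 9.2.1, so a range is assumed. Single-stage exact binomial power, with the rejection cutoff in brackets:

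| Assumed historical rate | n = 40, one-sided 0.05 | n = 40, two-sided 0.05 | n = 50, two-sided 0.05 |
|---|---|---|---|
| 30% | 0.79 (18) | 0.68 (19) | 0.76 (23) |
| 40% | 0.79 (22) | 0.69 (23) | 0.77 (28) |
| 50% | 0.81 (26) | 0.70 (27) | 0.78 (33) |
| 60% | 0.84 (30) | 0.73 (31) | 0.81 (38) |

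So 80% power for 20 points is roughly reachable in 50 patients with an exact test, but not from an effect size of 1.20 and an SD of 15%, and not two-sided in 40.

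**The case against.** The strongest reply is that the faulty sentence drives nothing. Accrual, stopping and rejection all come from 9.1, whose figures reproduce, and pCR is listed only as a secondary and an exploratory objective. That is true of the numbers. It does not make the sentence harmless, because 9.2.1 calls pCR the Phase II efficacy endpoint, attaches a significance level to it and names a test that cannot be run.

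A second reply is that 9.2.1 defines the effect size as a plain difference in pCR rate, without dividing by an SD, so the 20/15 check borrows the TIL definition. This is fair as a reading. But a raw difference of 1.20 would be 120 percentage points, so the sentence fails on either definition.

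Third, the conflict with 9.1 rests partly on inference. Section 9.1 never defines response, and no text says that 50 means the 10 Phase Ib plus 40 Phase II patients. The mention of both stages in 9.2.1 makes the link to pCR strong; the origin of the 50 remains a guess. Because response is undefined, 9.1 is not fully executable as printed either.

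Fourth, whether 10% is a sensible null is a design choice separate from the arithmetic, and the 50% benchmark is approximate. Section 1.3.2 does not say there that it is specific to TNBC, and some patients may go straight to surgery. This stands, and it is why the null is left to the sponsor below. The correction to 9.2.1 does not depend on it.

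**Conclusion.** The concern holds, and the statement must be corrected. The power figure in 9.2.1 does not follow from its inputs under any standard variant tried: 1.20 needs 8 patients, and 50 patients detect 0.40. The paired t-test and the 15% SD do not fit a single binary outcome per patient. The statement disagrees with 9.1 on sidedness, null and sample size. These conclusions need only the plan's own numbers, plus the reading that response in 9.1 means pCR.

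A further consequence depends on taking the roughly 50% in section 1.3.2 as the benchmark. At that true rate the 9.1 rule rejects with probability 0.9999 and almost never stops at stage 1, so it cannot show a gain over chemotherapy, which is the comparison section 1.3.2 gives as the purpose of Phase II. The powers for a 20-point gain rest on assumed historical rates of 30% to 60%.

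**What to change.** In 9.2.1, Phase II, delete the paired t-test, the effect size of 1.20, the SD of 15% and the 50-patient power claim. Name the two-stage exact binomial rule of 9.1, in 40 patients, as the only Phase II test of pCR, and state in 9.1 that response means pCR. The sponsor then chooses one of two aims.

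**(a) Keep the 9.1 rule.** State that it tests pCR only against 10%, and say in section 1.3.2 that the comparison with chemotherapy is descriptive. This costs wording only; n, cutoffs, alpha and power stay as they are. The price is that Phase II has no formal test against chemotherapy, and the stage 1 rule is nearly inert if pCR is near 50%.

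**(b) Test for a gain over a historical rate.** Print the rate and its source, state whether the test is one- or two-sided, and amend the null, both boundaries and the power in 9.1. As an example only, under an assumed 50% and a one-sided test: stop at 11 or fewer of 22 and reject at 26 or more of 40. This gives alpha 0.040, power 0.803 at 70%, and a stage 1 stopping probability of 0.584 at a true 50%. A two-sided test (reject at 27 or more) lowers power to 0.70. This is a design amendment, although n can stay at 40 in the one-sided example.

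Under either option, a confidence interval that allows for the two stages is optional good practice. The choice should be fixed before Phase II pCR results are examined.

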## STUDY SCHEMA

This is a prospective, phase Ib/II study of the preoperative combination of pembrolizumab (pembro) and radiation therapy (RT) in patients with operable breast cancer. Patients with newly diagnosed, Stage I-III breast cancer who are planned for breast-conserving surgery and adjuvant whole breast radiation therapy will be recruited into one of 2 cohorts as per their biomarker profile as depicted below. The TNBC cohort will have 50 subjects (10 TNBC subjects for phase Ib and 40 TNBC subjects for phase II) and the HR+ cohort will have 10 subjects. Enrollment will start with the phase Ib TNBC cohort. The trial will be conducted in a Bayesian design, wherein safety as assessed by lack of delay in standard of care treatment will be assessed after 3, 6, and 9 patients have initiated standard of care treatment in each cohort. Standard of care treatment is defined as breast-conserving surgery or initiation of neoadjuvant systemic chemotherapy. If the phase Ib TNBC trial meets a pre-specified safety endpoint, enrollment in

the phase II TNBC trial and HR+ cohort will take place.

Study treatment will consist of 2 doses of neoadjuvant pembro. The second dose will be given in combination with a RT boost. The primary objectives are: 1) to assess the feasibility of the preoperative combination of pembro and RT as defined by the number of patients who do not necessitate a delay in standard of care treatment, 2) to assess the change in tumor infiltrating lymphocyte (TIL) score with therapy. The secondary objectives are to describe the toxicity with preoperative pembro and RT up to 15 weeks after administration of pembrolizumab, to assess the invasive disease-free (iDFS) survival, and to assess the pathological complete response (pCR) rates.

- The first dose of pembro will be given on cycle 1, day 1 (C1D1). Each cycle will be 21 days. The second of pembro dose will be given on C2D1 (+/- 3 days).
- RT will be administered concurrently within one week of the second dose of pembro (C2D1 + 5 calendar days). 8Gy will be delivered in 3 fractions over 3 to 5 business days (for a total dose of 24Gy).
- Standard of care treatment, including breast-conserving surgery or additional neoadjuvant systemic therapy, will be pre-set to start 8 weeks after study enrollment (+/- 5 days).
- Research blood and stool will be obtained after consent up to C1D1. It will also be obtained on C2D1 (+/- 3 days) and at the time of initiation of standard of care treatment (+/- 5 days).

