### 3.0 STUDY DESIGN

#### ***Study Design***

This is a prospective, single-institution, Phase Ib/II study of the preoperative combination of pembrolizumab (pembro) and radiation therapy (RT) in patients with operable breast cancer (TNBC). The two cohorts will consist of 50 TNBC and 10 HR+ women each. Enrollment will start with the Phase Ib TNBC safety cohort. The trial will be conducted in a Bayesian design, wherein safety as assessed by lack of delay in standard of care treatment will be assessed after 3, 6, and 10 patients have initiated standard of care treatment. If at least 80% of the first 10 subjects in the TNBC cohort proceed with standard of care therapy without delay, the combination will be deemed safe in the cohort, and enrollment in the HR+ cohort, as well as continued enrollment in the TNBC cohort (40 subjects), will occur at that time.

Each cohort will be evaluated for delay in curative-intent standard of care treatment every time 3 patients complete study therapy and undergo standard of care treatment. At each of those timepoints, if the posterior probability that a patient experiences a delay in standard of care treatment exceeds 20%, the cohort will stop enrollment. In Bayesian statistics, the posterior probability of a random event or an uncertain proposition is the conditional probability that is assigned after the relevant evidence or background is taken into account. This design will assure that a cohort does not continue enrollment if early delays in standard of care treatment are seen. Enrollment will be carried out continuously and will not be stopped in order to evaluate the posterior probability of a delay. However, the number of patients undergoing assessment for a possible delay simultaneously will not exceed four in each of the 2 cohorts.

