## **9.0 STATISTICAL CONSIDERATIONS**

### **9.1 Sample Size**

#### **Phase Ib:**

It is imperative that any experimental pre-operative therapeutic innovation not undermine the timing of curative-intent treatment in localized breast cancer, the primary endpoint for the Phase Ib study is safety/tolerability, as defined by the number of patients who do not necessitate a delay in standard of care treatment (breast surgery or neoadjuvant systemic therapy followed by breast surgery). A small number of patients of TNBC will be included in this cohort to establish safety of the regimen as described below for consideration for further study. Along with safety, assessment of TILs through the course of treatment in this cohort will establish the immunogenicity of this combination. If at least 80% of the first 10 subjects in the TNBC cohort proceed with standard of care therapy without delay, the combination will be deemed safe in the cohort, and enrollment in the HR+ cohort (10 subjects) will occur at that time.

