#### **Phase II:**

Once the protocol has been determined to be safe and the protocol modified accordingly, we will employ Simon's two stage trial design. For this cohort, the null hypothesis that the true response rate is 10% will be tested against a one-sided alternative. In the first stage, 22 patients will be accrued. If there are 2 or fewer responses in these 22 patients, the study will be stopped. Otherwise, 18 additional patients will be accrued for a total of 40 patients. The null hypothesis will be rejected if 8 or more responses are observed in 40 patients. This design yields a type I error rate of 0.04 and power of 0.80 when the true response rate is 25%.

---

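### The Phase II pCR analysis is sized on 50 evaluable patients, but Phase II enrols 40 and the Simon rule is calibrated on those 40

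*Combined protocol and SAP*

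**What the plan says.** The Study Schema splits the TNBC patients by phase: "The TNBC cohort will have 50 subjects (10 TNBC subjects for phase Ib and 40 TNBC subjects for phase II". Section 3.0 agrees that, once the Phase Ib criterion is met, "continued enrollment in the TNBC cohort (40 subjects), will occur at that time". That criterion (Section 9.1, Phase Ib) concerns treatment timing, not response: "If at least 80% of the first 10 subjects in the TNBC cohort proceed with standard of care therapy without delay".

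Section 9.1, Phase II, sets a Simon two-stage design for the patients who follow: "the null hypothesis that the true response rate is 10% will be tested against a one-sided alternative". The interim look falls at 22 patients and carries this futility rule: "If there are 2 or fewer responses in these 22 patients, the study will be stopped". A trial that passes the look adds a second stage of 18, and the final criterion reads: "The null hypothesis will be rejected if 8 or more responses are observed in 40 patients". The stated properties are a type I error of 0.04 and power of 0.80 at a true rate of 25%.

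Section 9.2.1, Phase II, names pCR at surgery as the efficacy endpoint and refers to the trial passing through both stages. It then says: "Data from 50 evaluable patients achieve 80% power to detect an effect size". The value assumed there is 1.20, the test is a paired t-test (two-sided) against a historical TNBC rate, and the plan equates this with a 20-point difference and an SD of 15%.

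**The concern.** Sections 9.1 and 9.2.1 describe the same Phase II endpoint with different denominators. The TNBC total is 10 + 40, so a 50-patient TNBC analysis has to include Phase Ib. No sentence in Section 9 keeps the Phase Ib patients out of the pCR analysis. The general analysis set at the top of Section 9.2.1, everyone given a dose of study drug, would take them in.

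The Simon error rate holds only for the set on which it was computed. If the analyst settles the set when the analysis is done, the type I error depends on an unwritten counting rule, and the denominator could be chosen with pCR results in view.

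**Working it through.** **Inputs.** From Section 9.1: null rate 0.10, alternative 0.25, first stage 22 with a stop at 2 or fewer, second stage 18, reject at 8 or more of 40. From the Study Schema: 10 Phase Ib and 40 Phase II TNBC patients. From Section 9.2.1: n = 50, effect size 1.20, difference 20%, SD 15%. Section 9.1 does not define response. I take it to be pCR, because Section 9.2.1 names pCR as the Phase II efficacy endpoint.

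**1. The plan's own figure.** With b(x; 22, p) the binomial probability,

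P(reject) = Σ over x = 3 to 22 of b(x; 22, p) × P(Bin(18, p) ≥ 8 − x).

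This gives 0.0398 at p = 0.10 and 0.803 at p = 0.25. The stated 0.04 and 0.80 reproduce for 40 patients.

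**2. Where 50 can come from.** Phase II alone supplies 40. Adding Phase Ib gives 40 + 10 = 50, and only if every TNBC patient is evaluable. The 10 HR+ patients would also bring 40 to 50, but a TNBC historical comparator argues against that reading.

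**3. If the 10 were added with the bound left at 8.** This pooling rule is an assumption; it is not in the documents. Let k be the number of Phase Ib responders. If they count at the final analysis only,

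P(reject | k) = Σ over x = 3 to 22 of b(x; 22, p) × P(Bin(18, p) ≥ 8 − x − k).

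If they also count at stage 1, the sum runs over x + k ≥ 3. At p = 0.10:

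| k | P(k), Bin(10, 0.10) | Final count only | Both stages |
|---|---|---|---|
| 0 | 0.349 | 0.040 | 0.040 |
| 1 | 0.387 | 0.090 | 0.098 |
| 2 | 0.194 | 0.171 | 0.206 |
| 3 | 0.057 | 0.270 | 0.371 |
| Average over all k | | 0.102 | 0.121 |

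The averages are about 2.5 to 3 times the stated 0.04 and require no assumption about how many Phase Ib patients responded.

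**4. If the 10 were counted inside the 40.** With one Phase Ib responder the pass rate is 0.023 to 0.026. With the 10 placed in the first 22, the average over k stays at 0.040. The direction therefore depends on the counting rule.

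**5. A bound that fits 50.** Keep stage 1 on 22 new patients and add the 10 at the final count. Rejecting at 9 or more of 50 has average type I error 0.052. Rejecting at 10 or more of 50 has 0.023, with power 0.81 at 25%.

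**6. The power claim attached to the 50.** For a two-sided one-sample or paired t-test at 0.05, the noncentrality is 1.20 × √50 = 8.49 on 49 df, and power exceeds 99.9%. At that effect size n = 8 already gives 0.83. With n = 50, 80% power corresponds to an effect size of about 0.40. Also 20/15 = 1.33, not 1.20.

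**The case against.** The strongest reply is that the two numbers never meet. Section 9.1 ties the bound of 8 to 40 patients accrued after safety is established. Section 9.2.1 ties 50 to a separate t-test. The latter's wording closely follows the TIL power paragraph and does not reproduce, so a drafting slip is at least as likely as a plan to pool. This stands as far as the error rate goes: the written Simon rule has type I error 0.04. It does not remove the conflict, because a slip in the analysis set still needs correcting.

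The practical effect may also be small. Section 1.3.2 puts pCR with current chemotherapy at about 50%; at that rate the Simon rule passes more than 99.9% of the time with or without Phase Ib patients. This also stands, although the plan states its error rate at 10%, so that is where it has to hold.

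Pooling is not wrong in itself. With a bound set for 50 it is valid, as step 5 shows.

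A reader might infer that pooling would also bias a test against a 50% benchmark. It would not. An exact one-sided 0.05 test on 50 rejects at 32 or more, with size 3.2% over all 50 patients. Given 8 Phase Ib responders of 10 the pass rate is 13.4%, but that start has probability 45/1024 = 4.4% at a 50% rate. Given 5 of 10 the pass rate is 1.9%. Averaged over all starts it is 3.2% again.

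**Conclusion.** The conflict is real: one endpoint, two analysis sets, and a figure of 50 that Phase II enrolment cannot supply. The inflation to an average of 10% to 12% is conditional on two things that the documents do not state: that the 10 Phase Ib patients join the Simon count, and that the bound stays at 8. It also assumes that Phase Ib patients respond at the null rate of 10%.

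Two stronger readings are not supported. A reader might infer that the Simon rule already runs at 9% to 10%; no section applies the bound of 8 to 50 patients, and that range belongs only to the case of exactly one added responder. A reader might also infer that Phase Ib pCR will be in hand when Phase II opens. The gate concerns delay in starting standard of care, while pCR is read at surgery, in most cases after chemotherapy, so Phase II may open before those results exist. The averaged figures do not need that premise.

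This should be corrected before the pCR analysis; the written Simon design is not invalidated.

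**What to change.** In Sections 9.1 and 9.2.1, state that the stage 1 count, the final count and the pCR test use only the 40 TNBC patients enrolled after the Phase Ib go decision. Replace 50 with 40 in the Section 9.2.1 sentence. Restate its power for that set and for the Simon binomial test (type I error 0.04, power 0.80 at 25%) in place of the paired t-test claim. Report pCR in the 10 Phase Ib patients separately. A pooled 50-patient rate with its interval can be shown as descriptive, without a test.

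If the sponsor prefers to pool, write the pooling rule down and reset the bound. With stage 1 kept on 22 new patients, 10 or more of 50 gives type I error 0.023 and power 0.81 at 25%.

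The cost is a few sentences, with no new patients or data. The formal test rests on 40 rather than 50 patients, so its interval is slightly wider: at an observed rate of 50%, 1.96 × √(0.25/40) = 15.5 points either side, against 1.96 × √(0.25/50) = 13.9.

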#### **1.3.2 Clinical Data**

A systemic response to localized RT in combination with anti-CTLA-4 therapy, the so-called “abscopal effect”, was reported in a patient after disease progression with CTLA-4 blockade with ipilimumab alone. Specifically, a right hilar lymph node and spleen metastases, which was not the target of RT, showed regression only after the patient received palliative RT after several months of anti-CTLA-4.

Based on the above phenomenon as well as pre-clinical data suggesting the synergism of RT with immune therapies, studies evaluating the efficacy of RT with checkpoint blockade in metastatic breast cancer are actively ongoing. In a phase II study evaluating pembrolizumab and RT in metastatic TNBC patients, 2 out of 5 evaluable patients had a response outside of the irradiated field. Although assessing distant response is not one the endpoints of this protocol, which includes women with non-metastatic breast cancer, the study nevertheless provides proof-of-principle for the concept of systemic immune modulation by RT when added to checkpoint inhibition.

Once safety of the pembro-RT regimen has been established, the efficacy of the regimen remains to be tested. Current chemotherapy regimens (GeparSixto) report pathologic complete response

rates of approximately 50% and in the metastatic setting addition of atezolizumab (PD-L1) to nab-paclitaxel (IMpasion130) showed increased PFS in triple negative breast cancer. Based on these two recent observations, the phase II portion of this trial will test the efficacy of adding pembro-RT to neoadjuvant chemotherapy in early-stage breast cancer and determine the pathologic complete response rate in comparison to best available chemotherapy which is the current standard of care.

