## 2.4 Endpoints

- **Primary Efficacy Endpoint: Feasibility**

Feasibility will be defined by the number of patients who do not necessitate a delay in standard of care treatment. Since the combination of pembrolizumab and RT has not been tested in the preoperative setting in patients with potentially curative disease, it is necessary to establish whether such preoperative treatment can be safely given without delaying curative-intent treatment.

- **Co-Primary Efficacy Endpoint: Change in TILs**

An increase in TILs is an indicator of immune system engagement. A lead in with pembrolizumab alone followed by the combination of pembrolizumab with RT will allow for serial assessment of TILs. This will establish the contribution of RT to the immune response generated by pembrolizumab.

- **Safety Evaluations**

Immune related adverse events that result from checkpoint blockade can occur weeks after the drugs are administered. Therefore, adverse events will be recorded up to 15 weeks after administration of pembrolizumab and radiation therapy and graded according to CTCAE, Version 4.03. Immune related adverse events will also be documented for up to 1-year post treatment. When considering if an adverse event is immune related, a general principle is that differential diagnoses should be diligently evaluated according to standard medical practice. Non-inflammatory etiologies should be considered.

- **iDFS**

iDFS will be defined as the time from completion of surgery to the first occurrence of the following events: invasive ipsilateral, local, regional, or distant recurrence, or death due to breast cancer.

- **pCR**

pCR will be defined as the absence of invasive disease in the breast and lymph nodes at the time of curative-intent surgery.

---

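### Phase II names only paired tests for comparing responders with non-responders, who are different patients, so that comparison has no test that fits it

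*Combined protocol and SAP*

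**What the plan says.** The last paragraph of section 9.2.1 (Phase II) sets out the correlative analyses. It begins "Changes in TIL score, immune populations, gene expression, microbiome populations and cytokine expression will be compared" and says these are to be "compared between different time points and responder/non-responder groups if sufficient numbers for analysis are available using the paired t-test or Wilcoxon sign test", with the choice between the two tests left to the distribution of the data. One pair of tests therefore serves two comparisons: between time points, and between response groups.

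The paragraph does not define responder. The nearest definition is the pCR endpoint in section 2.4: "pCR will be defined as the absence of invasive disease in the breast and lymph nodes at the time of curative-intent surgery". On that reading each patient has one status, and the two groups share no patients.

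Section 9 names no unpaired t-test or rank-sum test. Its only between-group test for TIL change is Fisher's exact test, which is assigned to the comparison of cohorts, not of responders with non-responders.

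**The concern.** A paired test works on within-pair differences, so it needs a reason why one observation belongs with another. Time points supply that reason because the same patient is measured repeatedly. Responders and non-responders do not, and the plan describes no matching.

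An analyst who follows the sentence literally has two options. One is to find that the test cannot be run because the groups differ in size. The other is to invent pairs, drop whoever is left over, and report a p-value that depends on the pairing. An analyst who does neither must choose an unpaired test after the data are in hand, which a prespecified plan is meant to prevent. What is at stake is section 9's only stated method for relating TIL change and the immune, expression, microbiome and cytokine measures to response.

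**Working it through.** The disputed sentence carries no sample size or power of its own, so it has no figure to reproduce. As a check on the surrounding figures, the stated Simon design (22 then 40 patients, stop at 2 or fewer responses, reject at 8 or more) gives an exact type I error of 0.0398 and power of 0.803. These agree with the plan's 0.04 and 0.80.

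**Inputs**

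- Phase II size: 40, from section 9.1 ("18 additional patients will be accrued for a total of 40 patients").
- Response rates: 10%, from section 9.1 ("the null hypothesis that the true response rate is 10% will be tested against a one-sided alternative"); 25%, from the same section ("power of 0.80 when the true response rate is 25" per cent); and about 50%, the chemotherapy pCR rate in section 1.3.2 ("rates of approximately 50" per cent).
- Expected splits of 40: 0.10 × 40 = 4, so 4/36; 0.25 × 40 = 10, so 10/30; 0.50 × 40 = 20, so 20/20. The 8/32 split is added because 8 responses is the Simon rejection boundary.
- Significance level: 0.05 ("A significance of 0.05 will be used to declare statistical significance"), taken as two-sided.
- Assumptions not in the documents: responder means pCR, outcomes are normal with equal SD, and the true group difference is 1 SD.

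**Step 1: can the paired test be computed?** It needs equal groups. P(20 responders of 40) = C(40,20) × p^20 × (1 − p)^20.

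- p = 0.10: 1.7 × 10^-10, so below 0.0001
- p = 0.25: 0.0004
- p = 0.50: 0.125

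If the number of evaluable patients is odd, an equal split is impossible. Standard paired t-test and signed-rank routines, given groups of 10 and 30, return an error.

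**Step 2: what if pairs are forced at random?** Let m be the size of the smaller group; 40 − 2m patients are discarded. In 40,000 simulated trials per split with no true difference, type I error was 4.8% to 4.9%. For a difference of d SDs, power comes from the noncentral t distribution:

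- arbitrary pairing: noncentrality d × √(m/2), with m − 1 degrees of freedom
- unpaired: noncentrality d / √(1/n1 + 1/n2), with 38 degrees of freedom

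At d = 1:

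| Split | Discarded | Noncentrality, paired / unpaired | Power, arbitrary pairing | Power, unpaired |
|---|---|---|---|---|
| 4/36 | 32 | 1.41 / 1.90 | 17% | 46% |
| 8/32 | 24 | 2.00 / 2.53 | 41% | 69% |
| 10/30 | 20 | 2.24 / 2.74 | 51% | 76% |
| 20/20 | 0 | 3.16 / 3.16 | 85% | 87% |

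The simulation agreed with these figures to within half a percentage point. Because d is assumed, the same formulas at other values show the range. At d = 0.5 the pairs (arbitrary vs unpaired) are 8% vs 15% at 4/36, 17% vs 27% at 10/30 and 32% vs 34% at 20/20. At d = 1.5 they are 32% vs 79%, 85% vs 98% and 99% vs more than 99%.

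**Step 3: does the pairing matter?** In one simulated 20/20 data set the unpaired p-value was 0.003. Across 5,000 arbitrary pairings of the same data, the paired p-value ran from below 0.0001 to 0.028.

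**The case against.** The best reply is that the sentence is compressed. It may mean paired comparisons of time points within each response group, for which the named tests are right. That is a fair reading of the likely intent, since the same choice of tests is used correctly for the within-patient TIL comparison earlier in section 9.2.1. But the sentence does not say so, and that reading leaves the responder versus non-responder comparison with no test at all. The text needs correcting either way.

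A second reply is that nobody would actually pair unrelated patients: the software would refuse and the analyst would use an unpaired test. This is probably what would happen. The power losses above are therefore the cost of following the text literally, not a forecast. The likelier harm is a test chosen without prespecification.

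A third reply is that the loss is small when the groups are balanced, and most Phase II patients are expected to have had chemotherapy before surgery. This also stands: at 20/20 the loss is about 2 points. But even at a 50% rate an exact 20/20 split has a probability of only 0.125, and the plan's own design rates of 10% and 25% imply clear imbalance.

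A reader might go further and infer that the p-values would be invalid, in the sense of an inflated type I error. The documents do not support that. Random pairing holds the error near 5%. Simulated inflation to between 25% and 60% arose only when both groups were sorted and paired by rank, and nothing in the plan suggests doing so.

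**Conclusion.** The point holds as a misspecified secondary analysis. The only tests named for a comparison of independent groups are paired tests; they will usually not be computable, and when forced they lose data and give a p-value that depends on an arbitrary choice. For an assumed 1-SD difference the power loss runs from about 2 points at an even split to 29 points at 4/36 (46% − 17%). That size rests on the assumed difference, normality, equal SDs and all 40 patients being evaluable. The mismatch between test and groups rests on none of these, nor on responder meaning pCR: any classification that gives each patient one status produces separate groups.

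A reader might also infer that the main Phase II result is undermined. It is not. The Simon rule on pCR does not use this test, and the co-primary TIL analysis is a within-patient comparison for which pairing is appropriate. The affected comparison is conditional on adequate numbers and is correlative; immune composition, transcriptome, microbiome and cytokines sit under the exploratory objectives in section 2.3. The correction should be made, but no enrolment or stopping decision depends on it.

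**What to change.** Split the sentence in section 9.2.1 (Phase II) in two:

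- Within-patient comparisons between time points: paired t-test or Wilcoxon signed-rank test. Naming the signed-rank test also settles whether Wilcoxon sign test means that or the simpler sign test.
- Responders versus non-responders: two-sample (Welch) t-test or Wilcoxon rank-sum test, applied to one value or one change per patient.

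In the same edit, state that responder means pCR as defined in section 2.4, if that is what is intended. The cost is a short text amendment, with no change to design, sample size or data collection.
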